If subjects progress during the clinical follow-up period or the survival follow-up period, they could further receive therapy with relatlimab alone or in combination with nivolumab (Re-challenge) as long as the risk:benefit ratio is considered favorable by the Investigator and the Medical Monitor and the following eligibility criteria is met: 1) Subject has confirmed disease progression 2) Subject has not experienced relatlimab related adverse events leading to permanent discontinuation. The original dose and schedule of therapy and protocol rules will apply. Thus subjects could receive therapy for up to 6 additional eight-week cycles.

Subjects who are re-challenged and who subsequently have an objective response will not be included in the primary analysis of efficacy. Responses to re-challenge will be evaluated in a separate analysis. Subjects will not be re-challenged a second time.

Dose-Limiting Toxicities:

For the purpose of guiding decisions regarding dose escalation in Part A, (DLT) will be determined based on the incidence, intensity, and duration of AEs that are related to study drug and that occur within 8 weeks of initiation of study drug (ie, the DLT evaluation interval which begins on the first day of treatment and ends on Day 56 of the first cycle).

For the purpose of guiding decision in combination dose escalation in Part C, (DLT) will be determined based on the incidence, intensity, and duration of AEs that are related to study drug and that occur within 4 weeks of initiation of study drug (ie, the DLT evaluation interval which begins on the first day of treatment and ends on Day 29 of the first cycle).

Adverse events will be graded according to the National Cancer Institute (NCI) Common Terminology Criteria for Adverse Events version 4.0 (CTCAE v4.0). For the purpose of subject management, any AE that meets DLT criteria, regardless of the cycle in which it occurs, will lead to dose interruption.

Dose escalation will be based on the number of DLTs experienced during the DLT evaluation interval as determined by the Medical Monitor and Investigators.

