No intra subject dose escalation is allowed. In Part A, subjects who receive at least 1 dose of study drug during the 8-week evaluation interval will be considered evaluable for DLT determination. In Part C, subjects who receive at least 2 doses of study drug during the 4-week evaluation interval will be considered evaluable for DLT determination. Subjects who withdraw from the study during the DLT evaluation interval for reasons other than a DLT and/or for whom safety data are unavailable for the entire DLT evaluation interval may be replaced at the same dose level. In the event that an infusion cannot be administered at a scheduled visit during the DLT evaluation interval, it must be administered as soon as possible. If the delay is between 1 and 7 days, the procedures at the originally scheduled visit should be performed and subjects will be considered evaluable for DLT determination. If the delay is more than 7 days, the dose will be considered missed and will not be replaced. Subjects with a delay of more than 7 days will not be considered evaluable for DLT determination. Unevaluable subjects may be replaced at the same dose level.

Duration of Study: Subjects will be allowed to continue on therapy for up to twelve 8-week cycles or confirmed PD or until meeting criteria for discontinuation as described in [Section 3.5](#). Treatment beyond progression may be considered in select subjects as described in [Section 4.3.4](#). Subjects may be on study for a total of up to approximately 5 years, including a 28-day screening period, up to twelve 8-week cycles of treatment, a 135-day clinical follow-up period, and up to 5 years of follow-up for survival (beginning from the first dose of study drug). The study will end once survival follow-up has concluded. For WOCBP, additional home pregnancy tests through Day [REDACTED]. The total duration of the study is expected to be approximately 9-10 years from the time of the first visit of the first subject to the required survival follow-up of the last subject enrolled. If subjects progress during the clinical follow-up prior or the survival follow-up period, could further receive therapy with relatlimab alone or in combination with nivolumab (Re-challenge) as long as they meet eligibility criteria and the risk:benefit ratio is considered favorable by the Investigator and the Medical Monitor. The original dose and schedule and protocol rules would apply accordingly. Subjects will not be re-challenged a second time.

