3.1.6 Dose-Limiting Toxicities

For the purpose of guiding decisions regarding dose escalation in Part A, dose-limiting toxicity (DLT) will be determined based on the incidence, intensity, and duration of AEs that are related to study drug and that occur within 8 weeks of initiation of study drug (ie, the DLT evaluation interval which begins on the first day of treatment and ends on Day [REDACTED] of the first cycle).

For the purpose of guiding decision in combination dose escalation in Part C, dose-limiting toxicity (DLT) will be determined based on the incidence, intensity, and duration of AEs that are related to study drug and that occur within 4 weeks of initiation of study drug (ie, the DLT evaluation interval which begins on the first day of treatment and ends on Day [REDACTED] of the first cycle).

The severity of AEs will be graded according to National Cancer Institute (NCI) Common Terminology Criteria for Adverse Events (CTCAE) v4.0.

For the purpose of subject management, DLTs that occur at any time, whether during dose escalation (Part A or C) or cohort expansion (Part B or D) will result in study drug being held pending evaluation of the event's relatedness to study drug in accordance with [Section 4.3.2](#). Subjects must meet criteria for re-treatment prior to re-initiation of study treatment (see [Section 4.3.3](#)).

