In Part A, subjects who receive at least 1 dose of relatlimab during the 8-week evaluation interval will be considered evaluable for DLT determination. In Part C, subjects who receive at least 2 doses of relatlimab and nivolumab during the 4-week evaluation interval will be considered evaluable for DLT determination. In the event that study drug cannot be administered at a scheduled visit during the DLT evaluation interval, it must be administered as soon as possible. If the delay is between 1 and 7 days, the procedures at the originally scheduled visit should be performed and subjects will be considered evaluable for DLT determination. If the delay is more than 7 days, the dose will be considered missed and will not be replaced. Subjects with a delay of more than 7 days will not be considered evaluable for DLT determination. Unevaluable subjects may be replaced at the same dose level. Subjects who miss a dose during the DLT evaluation period may continue on treatment if the subject does not otherwise meet the criteria for permanent discontinuation in [Section 4.3.5](#).

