4.3.2 Dose Delay Criteria

In some cases, the natural history of select AEs associated with immunotherapy can differ from and be more severe than AEs caused by other therapeutic classes. Early recognition and management may mitigate severe toxicity.

Guidance for Investigators is provided in the current relatlimab and nivolumab Investigator's Brochures.^{58.14} Additionally, management algorithms have been developed to assist Investigators with select toxicities and can be found in [Appendix 4](#).

Toxicities for which management algorithms have been developed include:

- Pulmonary.
- Gastrointestinal.
- Hepatic.
- Endocrine.
- Renal.
- Dermatologic.
- Neurologic.
- Myocarditis.

Subjects who experience the following must have all study drugs(s) delayed:

- Potential DLTs (per definition, are related to study drug) until DLT relatedness is defined.
- Select drug-related AEs and drug-related laboratory abnormalities:
 - \geq Grade 1 pneumonitis.
 - \geq Grade 1 myocarditis.
 - All troponin elevations require a dose delay to allow for prompt cardiac evaluation.
 - \geq Single grade increase shift from baseline (at least to Grade 2) of AST, ALT, and total bilirubin.
 - \geq Grade 2 creatinine.
 - \geq Grade 2 diarrhea or colitis.
 - \geq Grade 2 neurological AE.
 - Grade 4 amylase and/or lipase abnormalities regardless of symptoms or clinical manifestations.
- Any AE, laboratory abnormality, or intercurrent illness, which in the judgment of the Investigator, warrants delaying the dose of study medication.

Subjects may be dosed no less than █ days from the previous dose and no more than █ days from scheduled dose. If an infusion cannot be administered at a scheduled visit, it should be administered as soon as possible. Subsequent dosing visits will follow every █ weeks after the delayed dose. A dose given more than █ days after the intended dose date will be considered a delay. A maximum delay of █ weeks between doses is allowed. Longer delays may be allowed following discussion with the Medical Monitor. Subjects who meet criteria listed in [Section 4.3.5](#) are required to permanently discontinue study drug. All other subjects will be permitted to resume therapy with study drug at the same dose level(s) following resolution of the AE as described in Section 4.3.3.

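### In Part C, a DLT that stops the second dose can make the subject unevaluable for DLT, because the evaluability rules have no exception for it

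*Combined protocol and SAP*

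**What the plan says.** The evaluability rules stand at the end of Section 3.1.6.1 and, in nearly the same words, in the synopsis under Dose-Limiting Toxicities.

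- Part A: "In Part A, subjects who receive at least 1 dose of relatlimab during the 8-week evaluation interval will be considered evaluable for DLT determination". Section 3.1.1 repeats this one-dose rule and gives no delay rule.
- Part C: "subjects who receive at least 2 doses of relatlimab and nivolumab during the 4-week evaluation interval will be considered evaluable for DLT determination".
- Delay rule, not limited to either part: "Subjects with a delay of more than 7 days will not be considered evaluable for DLT determination". A dose more than 7 days late counts as missed and is not made up.
- Replacement: "Unevaluable subjects may be replaced at the same dose level".

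Other sections say what a DLT does to dosing. The synopsis says that "any AE that meets DLT criteria, regardless of the cycle in which it occurs, will lead to dose interruption". Section 3.1.6 says that DLTs at any time "will result in study drug being held pending evaluation of the event's relatedness to study drug". Section 4.3.2 lists among the mandatory reasons for delay: "Potential DLTs (per definition, are related to study drug) until DLT relatedness is defined". Section 4.3.5 requires permanent discontinuation for many events of DLT type, for example Grade 3 drug-related myocarditis or pneumonitis of any duration. It also expects permanent discontinuation in most cases of AST or ALT elevation that meets DLT criteria.

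The escalation steps in Section 3.1.1 count DLTs among evaluable subjects. Section 3.1.3 applies the same steps to Part C with a 4-week window. The synopsis gives Day 29 as the end of that window.

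**The concern.** Evaluability is defined by doses received and delay, and a DLT itself reduces doses and causes delay. Membership of the denominator therefore depends on the outcome being counted. A subject without toxicity who receives both doses stays in. A subject whose toxicity stops the second dose can fall out and be replaced by someone who may have no DLT. The observed DLT rate can then only move downward.

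DLTs and the MTD belong to the primary objective in Section 1.3.1, and the Part C MTD or MAD caps the Part D dose. Section 8.2 defines no DLT population, so the sentences quoted above are the only definition of who counts.

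**Working it through.** **Part C, rule against rule**

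1. Dosing is every two weeks, so dose 1 is on Day 1 and dose 2 on Day 15.
2. Suppose a DLT occurs after dose 1 and before Day 15. Study drug must be held.
3. If the event requires permanent discontinuation, the subject never receives a second dose and fails the two-dose rule.
4. If dosing is only held, the Day 15 dose may be given up to Day 22 (15 + 7) and the subject stays evaluable. After Day 22 the dose is missed and the subject is not evaluable.
5. The escalation steps count evaluable subjects, so in step 3, and in step 4 when the hold runs past Day 22, the DLT leaves the count.
6. A DLT after the Day 15 dose finds the two-dose rule already met. The text does not say whether a held Day 29 dose would trigger the delay rule, since Day 29 is the end of the window. I do not rely on that case. The clear exposure is DLTs before dose 2.

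**Part A, rule against rule**

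A subject with one dose and a DLT is evaluable under the one-dose rule. The same subject, with the next dose more than 7 days late, is not evaluable under the delay rule. Section 3.1.6.1 also says that a subject who progresses during the DLT period is no longer evaluable, without saying what applies if a DLT came first. The three statements cannot all hold.

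**Illustration of size**

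The documents give no readable operating characteristic for escalation, so there is no stated figure to reproduce. Section 3.1.1 shows an initial cohort of three and expansion after one DLT; the other limits are redacted.

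Assumed limits: escalate on 0/3, on at most 1/6 or on 2/9; stop on at least 2/3, 3/6 or 3/9. Let p be the true DLT rate and f the fraction of DLT subjects ruled unevaluable and replaced.

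- DLT rate among evaluable subjects: q = p(1 − f)/(1 − pf).
- With b0 = (1 − q)³ and b1 = 3q(1 − q)², P(escalate) = b0 + b1·b0 + b1²·b0 = b0(1 + b1 + b1²).

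For p = 0.33:

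- f = 0: q = 0.33, b0 = 0.301, b1 = 0.444, P = 0.301 × 1.642 = 0.494.
- f = 0.25: q = 0.2475/0.9175 = 0.270, b0 = 0.389, b1 = 0.432, P = 0.630.
- f = 0.50: q = 0.165/0.835 = 0.198, b0 = 0.517, b1 = 0.382, P = 0.789.

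| True DLT rate | f = 0 | f = 0.25 | f = 0.50 |
|---|---|---|---|
| 33% | 0.494 | 0.630 | 0.789 |
| 40% | 0.350 | 0.487 | 0.675 |
| 50% | 0.189 | 0.298 | 0.487 |

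With a laxer final limit (stop only at 4/9 or more), the 33% row becomes 0.582, 0.710 and 0.845. The direction is the same.

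One cohort shows the mechanism. Under the assumed limits, two DLTs in the first three subjects stop escalation. If one of those subjects is ruled unevaluable and the replacement has no DLT, the count is 1/3 and the cohort expands instead.

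**The case against.** The best defence is that the intent is plain. DLTs are defined as related events in the window, and escalation rests on the number of DLTs as judged by the Medical Monitor and investigators. Replacement is only permitted. The synopsis lets a withdrawn subject be replaced when the reason was something other than a DLT, which suggests that DLT cases were meant to stay. This is good evidence of intent, but it does not close the gap. The carve-out covers withdrawal from the study, not held or missed doses, and it is absent from Section 3.1.6. Loss of evaluability after a long delay is mandatory even though replacement is optional.

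A second defence is that escalation is largely over. The monotherapy MTD was not reached, the Part D combination is chosen, and cohorts beyond Dose Cohort 3 need an amendment. That stands in part. Section 3.1.3 still allows expanded or intermediate cohorts, and DLT rates and the MTD/MAD have yet to be reported.

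Third, the events are not lost to safety reporting. Safety summaries use all treated subjects, and Part D monitors DLT-type toxicity across all treated subjects. This stands. The risk is to the escalation count and the MTD/MAD.

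A reader might infer three stronger things that the documents do not support:

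- That DLT subjects were dropped. No passage shows this. The nine additional patients mentioned in Section 3.1.6.1 are attributed to progression.
- That the hepatic criterion requiring two weeks without recovery breaches the 7-day limit by itself. It does not, because the limit runs from the scheduled dose. Onset on Day 3 reaches two weeks on Day 17, when the Day 15 dose is 2 days late. Onset on Day 8 reaches it on Day 22, 7 days late and still evaluable.
- That Part A clearly loses DLTs. Its one-dose rule would keep them, so the problem there is a contradiction.

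**Conclusion.** The point holds for Part C as a defect in a stated rule. Followed literally, a DLT that prevents the Day 15 dose, or delays it by more than 7 days, makes the subject unevaluable and allows the DLT to leave the escalation count and the MTD/MAD determination. The resulting bias is downward. For Part A, the one-dose rule, the delay rule and the statement on progressors must be reconciled.

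The direction follows from the text. The size does not: the rises from 49% to 63% and 79% at a true rate of 33% rest on assumed cut-offs, an assumed true rate, independent subjects, replacement of every dropped subject, and an unknown dropped fraction. Not every DLT is exposed, and nothing in the documents supports a particular value of that fraction.

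**What to change.** Add to Section 3.1.6 and the synopsis: any subject with a DLT in the evaluation interval is DLT-evaluable, is counted and is not replaced, whatever the number of doses received or the length of delay; the minimum-dose and more-than-7-day exclusions apply only to subjects without a DLT. In the same edit, reconcile the Part A one-dose rule with the delay rule and with the statement on progressors in Section 3.1.6.1.

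Before DLT rates and the MTD/MAD are reported, re-check every Part A and Part C subject already replaced against the new wording.

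The cost is one paragraph in two places and a review of the replaced subjects. The downside is that a reported DLT rate may become slightly less favourable. The added wording changes who is counted and sets no dose, hold or discontinuation rule.

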3.2 Post Study Access to Therapy

At the end of the study, BMS will not continue to supply study drug to subjects/investigators unless BMS chooses to extend the study. The investigator should ensure that the subject receives appropriate standard of care to treat the condition under study.

3.3 Study Population

For entry into the study, the following criteria **MUST** be met prior to dosing on Day 1. No exceptions will be granted.

3.3.1 Inclusion Criteria

1) Signed Written Informed Consent

- a) The subject must sign and date the IRB/IEC-approved written informed consent form prior to the performance of any study-related procedures that are not considered part of standard of care.
- b) Consent for biopsy samples in subjects with Lymphoma.
 - i) Subjects must consent to allow a pre-treatment tumor biopsy (eg, lymph node) to be performed (all subjects). If a pre-treatment tumor biopsy is not clinically feasible, subject must consent to allow the acquisition of an archived tumor sample (eg, primary tumor, lymph node, etc). Subjects unable to provide a fresh pre-treatment tumor biopsy or archived tumor sample must seek approval of the BMS Medical Monitor before

- enrolling. Subjects whose pre-treatment biopsy yields inadequate tissue quantity or quality will not be ineligible on this basis alone.
- ii) Subjects enrolled in Part B and C with Hodgkin lymphoma whose disease progresses while-on or within 3 months of treatment with anti-PD-1 or anti-PD-L1 antibody must consent to allow a pre-treatment tumor biopsy (eg, lymph node) to be performed. If a pre-treatment tumor biopsy is not clinically feasible, subject must consent to allow the acquisition of an archived tumor sample (eg, primary tumor, lymph node, etc) collected after the most recent therapy. Subjects unable to provide a fresh pre-treatment tumor biopsy or archived tumor sample must seek approval of the BMS Medical Monitor. Subjects whose pre-treatment biopsy yields inadequate tissue quantity or quality will not be ineligible on this basis alone.
 - iii) The first three subjects in each cohort enrolled in the Part C, dose escalation, must consent to allow on-treatment tumor biopsy (eg, lymph node) to be performed at Week 4 during cycle 1 independently of the disease status. Subjects unable to provide a fresh on-treatment tumor biopsy must seek approval of the BMS Medical Monitor.
 - iv) All subjects in Part D must consent to allow on-treatment tumor biopsy (eg, lymph node) to be performed at Week 4 during cycle 1 independently of the disease status. Note: If a fresh pre-treatment tumor biopsy was not medically feasible and enrollment was approved by the Medical Monitor, the on-treatment tumor biopsy will not be required.
 - v) Subjects enrolled in Part A and B must consent to allow a pre-treatment unilateral bone marrow biopsy and/or aspirate to be performed (all subjects). Subjects who had a bone marrow biopsy and/or aspirate since completion of their last therapy may not use those results in lieu of the required baseline bone marrow biopsy.
 - vi) Subjects enrolled in the [REDACTED] mg monotherapy escalation cohort must consent to allow on-treatment unilateral bone marrow biopsy and/or aspirate to be performed at Week 4 during cycle 1 independently of the disease status. Subjects unable to provide a fresh on-treatment tumor biopsy are not eligible.
 - vii) Subjects enrolled in the [REDACTED] mg monotherapy escalation cohort must consent to allow on treatment unilateral bone marrow biopsy and/or aspirate to be performed to document complete response (CR), partial response (PR), or progressive disease (PD) shall be performed as clinically indicated.
 - viii) Subjects enrolled in Part B, expansion monotherapy cohort, must consent to allow on-treatment unilateral bone marrow biopsy and/or aspirate to be performed (first three subjects in each cohort) at Week 4 during cycle 1 independently of the disease status. Subjects unable to provide a fresh on-treatment tumor biopsy are not eligible.
 - ix) Subjects enrolled in Part B, expansion monotherapy, must consent to allow on treatment unilateral bone marrow biopsy and/or aspirate to be performed to document

complete response (CR), partial response (PR), or progressive disease (PD) shall be performed as clinically indicated.

- c) Consent for biopsy samples in subjects with Multiple Myeloma.
 - i) Subjects must consent to allow a pre-treatment unilateral bone marrow biopsy and/or aspirate to be performed (all subjects).

2) Target Population

- a) Subjects must have histologic or cytologic confirmation of chronic lymphocytic leukemia, Hodgkin lymphoma, Non-Hodgkin lymphoma, or Multiple Myeloma and have relapsed following prior treatment or been refractory to prior treatment.
- b) Part A Dose Escalation Relatlimab Monotherapy.
 - i) Chronic lymphocytic leukemia.
 - ii) Hodgkin lymphoma.
 - iii) Non-Hodgkin lymphoma.
 - iv) Multiple Myeloma by modified IMWG Criteria⁶³ (Appendix 6).
- c) Part B Cohort Expansion Relatlimab Monotherapy [REDACTED] mg.
 - i) Chronic lymphocytic leukemia.
 - ii) Diffuse large B-cell lymphoma.
 - iii) Indolent non-Hodgkin lymphoma.
 - iv) Hodgkin Lymphoma.
- d) Part C Dose Escalation Relatlimab in Combination with Nivolumab.
 - i) Hodgkin Lymphoma.
 - ii) Diffuse Large B-Cell Lymphoma.
- e) Part D Dose Expansion Relatlimab in Combination with Nivolumab.
 - i) Hodgkin Lymphoma naive to anti-PD-1/PD-L1.
 - ii) Hodgkin Lymphoma whose disease progresses while-on or within 3 months of treatment with anti-PD-1 or anti-PD-L1 antibody as most recent therapy.
 - iii) Diffuse Large B-Cell Lymphoma.
- f) In Part A, and selected cohort in Part D, (ie, Hodgkin Lymphoma anti-PD-1/PD-L1 naive cohort), only subjects without prior exposure to immune cell-modulating antibody regimens (ICMARs), such as but not limited to anti PD-1, anti PD-L1, anti PD-L2, anti CTLA-4, anti-KIR, and/or anti-OX40 antibodies, are allowed. Prior anti-CD20, alemtuzumab, and/or anti-CD30 antibody therapy is allowed.

In Part B, Part C, and selected cohort in Part D (ie Hodgkin Lymphoma subjects who progresses while on or within 3 months of treatment with anti PD-1/PD-L1 as most recent

therapy and Diffuse Large B-Cell Lymphoma subjects), only subjects without prior exposure to immune cell-modulating antibody regimens (ICMARs), such as, but not limited to anti-CTLA-4, anti-CD137, anti PD-L2, anti-KIR, and/or anti-OX40 antibodies are allowed. Prior anti-PD-1, anti-PD-L1, anti-CD20, alemtuzumab, and/or anti-CD30 antibody therapy is allowed.

g) Definition of Measurable Disease.

- i) Subjects with lymphomas and CLL must have at least one measureable lesion > 1.5 cm as defined by the Lymphoma (Revised Response Criteria for Malignant Lymphoma)⁶³ and CLL (Guidelines for the Diagnosis and Treatment of Chronic Lymphocytic Leukemia)⁶² response criteria (Appendices 1 and 2). Tumor sites that are considered measureable must not have received prior radiation therapy.
- h) Subjects must have progressed or been refractory to, at least one prior standard therapy, including radiation, immunomodulatory agents (eg, lenalidomide), immunotherapy, cytotoxic chemotherapy, and select antibody (anti-CD20, alemtuzumab, or anti-CD30) therapy. The following are not considered separate lines of treatment: addition of a compound to an ongoing regimen, restarting the same regimen after a drug holiday, or switching from IV to oral therapy.
- i) Subjects are not eligible for transplantation or any standard therapy known to be life-prolonging or life-saving. (Subjects who are eligible for transplantation or any standard therapy known to be life-prolonging or life-saving and who have declined transplantation or any standard therapy known to be life-prolonging or life-saving are eligible for the study.)
- j) Subjects must be more than 100 days post autologous transplant.
- k) Eastern Cooperative Oncology Group (ECOG) status of 0 or 1.
- l) Life expectancy of ≥ 10 weeks at the time of informed consent per Investigator assessment.
- m) Adequate organ function as defined by the following:
 - i) Neutrophils $\geq 750/\mu\text{L}$ (stable off any growth factor within 2 weeks of first study drug administration).
 - ii) Platelets $\geq 50 \times 10^3/\mu\text{L}$ (transfusion to achieve this level is not permitted within 2 weeks of first study drug administration).
 - iii) Hemoglobin ≥ 8.5 g/dL (transfusion to achieve this level is not permitted within 1 week of first study drug administration).
 - iv) Creatinine $< 1.5 \times \text{ULN}$ or creatinine clearance ≥ 40 mL/min (Cockcroft-Gault formula).
 - v) ALT and AST $\leq 3 \times \text{ULN}$.

- vi) Total bilirubin $\leq 1.5 \times \text{ULN}$ (except subjects with Gilbert's syndrome who must have a total bilirubin level of $< 3.0 \times \text{ULN}$).
- vii) Normal thyroid function, or stable on hormone supplementation per Investigator assessment.
- n) Ability to comply with treatment, PK, and pharmacodynamic sample collection and required study follow-up.
- o) Subject re-enrollment: This study permits the re-enrollment of a subject that has discontinued the study as a pre-treatment failure (ie, subject has not been randomized or treated). If re-enrolled, the subject must be re-consented.
- p) Adequate cardiac function as defined by the following:
 - i) LVEF $\geq 50\%$ by either TTE or MUGA (TTE preferred test) within 6 months of first drug administration.

3) Age and Reproductive Status

- a) Men and women, ages ≥ 18 years at the time of informed consent.
- b) Women of childbearing potential (WOCBP) must have a negative serum or urine pregnancy test (urine pregnancy test: minimum sensitivity 25 IU/L or equivalent units of human chorionic gonadotropin [hCG]) within 24 hours prior to the start of study drug.
- c) Women must not be breastfeeding.
- d) WOCBP must agree to follow instructions for method(s) of contraception for the duration of treatment with relatlimab plus 5 half-lives of relatlimab (135 days) plus 30 days (duration of ovulatory cycle) for a total of 165 days (24 weeks) after completion of treatment. The terminal half-life of nivolumab is up to 25 days. WOCBP who are treated with combination of relatlimab and nivolumab should follow the requirements for relatlimab which has a slightly longer half-life than nivolumab.
- e) Men who are sexually active with WOCBP must agree to follow instructions for method(s) of contraception for the duration of treatment with relatlimab plus 5 half-lives of relatlimab (135 days) plus 90 days (duration of sperm turnover) for a total of 225 days (33 weeks) after completion of treatment. Those treated with the combination of relatlimab and nivolumab should follow the requirements for relatlimab which has a slightly longer half-life than nivolumab.
- f) Azoospermic males and WOCBP who are continuously not heterosexually active are exempt from contraceptive requirements. However, WOCBP who abstain from heterosexual activity on a continuous basis must still undergo pregnancy testing as described in this protocol.

Investigators shall counsel WOCBP and male subjects who are sexually active with WOCBP on the importance of pregnancy prevention and the implications of an unexpected pregnancy. Investigators shall advise WOCBP and male subjects who are sexually active with WOCBP on the

use of highly effective methods of contraception. Highly effective methods of contraception ([Appendix 3](#)) have a failure rate of < 1% per year when used consistently and correctly.

